4.4 EXPLORATORY ENDPOINTS ANALYSES

Exploratory efficacy endpoints are:

- HBV dynamic biomarkers: quantitative anti-HBc (IgG or total), quantitative total HBsAg (post dissociation of HBsAg/HBsAb complexes)
- HBV genome sequencing: HBV RNA sequencing, HBV DNA sequencing

If available, these data will be listed at a minimum. Additionally, plots and summary statistics will be produced by treatment arm as appropriate.

Relapse Rate:

Relapse rate where HBsAg loss achieved at EOT or during follow-up period but rebounded at primary timepoint (24 weeks post-EOT), will be calculated for primary endpoint.

Subgroup Exploratory Analysis:

The association between virological outcome (HBsAg, HBeAg, HBV-DNA, HBV-RNA, HBcrAg) and baseline HBsAg stratification, baseline HBeAg status, clinical genotype (if available), gender, ethnicity will be explored graphically. Subsequent exploratory analyses may be performed at end of study or during study.

4.5 SAFETY ANALYSES

All safety analyses will be based on the safety analysis population grouped according to the treatment assigned at randomization.

The safety data, including AEs, reasons for withdrawal from treatment and study, laboratory data, ECGs, concomitant medications, vital signs, and physical examination results will be listed and summarized descriptively. Marked abnormalities will be flagged for laboratory data. As appropriate, listings, summary tables and graphs (participant plot and/or mean plots) will be provided for safety and tolerability assessments.

Key Definitions:

Modified Injection Site Reaction: A modified ISR will be defined as, an ISR for which the criteria for a 4-hour post dose injection site reaction is met.

4.5.1 Extent of Exposure

For safety-evaluable participants, study drug administration data will be tabulated or listed by treatment arm within each stage, and any dose modifications will be flagged. Tables and listings will be provided for individual participants by actual received

Combination Therapies for CHB—F. Hoffmann-La Roche Ltd Statistical Analysis Plan WV41073

treatment and exposure to NME or NME combinations or NUCs. The duration of study drug administration, actual cumulative dose and percentage of actual cumulative dose in planned cumulative dose will be summarized by treatment. A patient listing of study drug administration by center/patient number will also be provided.

4.5.2 Adverse Events

Tables and listings will be presented with respect to;

- All clinical adverse events (AEs), summarized
- Serious adverse events (SAEs), and
- Adverse events of special interest (AESI)
 - Cases of elevated ALT or AST (> 3 × ULN and >3 × baseline) in combination with either an elevated total bilirubin (> 2 × ULN) or clinical jaundice (Potential Hy's law)
 - Suspected transmission of an infectious agent by the study treatment, as defined below:
 - Any organism, virus, or infectious particle (e.g., prion protein transmitting transmissible spongiform encephalopathy), pathogenic or non-pathogenic, is considered an infectious agent. A transmission of an infectious agent may be suspected from clinical symptoms or laboratory findings that indicate an infection in a participant exposed to a medicinal product. This term applies only when a contamination of the study treatment is suspected.
 - ALT or aspartate aminotransferase (AST) elevations ≥ 10 x ULN
 - Grade ≥3 hematology lab abnormalities (e.g., lymphopenia, neutropenia, leukopenia)
 - Severe/serious injection site reactions and/or injection reactions
- AEs will also be summarized by grade and causal relationship to the applicable study drug(s) part of the combination, as judged by the investigator
- AEs leading to dose interruptions or study drug adjustments
- Adverse events leading to withdrawal from the study treatment/study
- Listing of participants with Grade 2 blood cell count decreases or any infections Grade 2 intensity or higher.

The original terms recorded on the eCRF by the investigator for adverse events will be standardized by the sponsor. Reported AEs will be coded to preferred terms and body

systems as defined by the latest version of the Medical Dictionary for Regulatory Activities (MedDRA). Some AEs may be summarized by gender if required.

The adverse event severity grading scale for the DAIDS (v2.1) will be used for assessing severity for adverse events. For detail of the grading scale, please refer section 3.1 of the protocol.

Glossaries of the body systems, preferred terms and verbatim terms for all AEs and subgroups of AEs of special interest will be provided.

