Due to strict lockdowns and restrictions in China in March - May 2022, as of 31 May 2022 approximately 30-53% of participants in each treatment arm have missed study visits and siRNA drug administration at the site. As a result, a number of participants have consecutive visits missed with potential impact on the evaluation of the primary endpoint due to incomplete data. To preserve the viability of the study, if COVID-19 restrictions continue, or any future COVID-19 outbreaks or any force majeure (e.g. natural disasters, supply chain disruption, outbreak of hostilities etc.) impacting participants, will lead to additional participants being recruited to the study to ensure

that the number of participants per treatment arm with the full dose as per the randomized dose regimen remains approximately 30 (see Section 9.2). The maximum number of additional participants to be recruited will be approximately 30 for each treatment arm (see Section 9.2).

Randomization will also take into account arm-specific exclusion criteria of actively enrolling arms. Participants will be ineligible for a specific arm if they meet any of the exclusion criteria outlined for that arm (please see arm specific appendix). Details on treatment assignment and randomization are provided in Section 6.4.1

The primary endpoint is the proportion of participants with HBsAg loss at 24 weeks post-EOT as defined in Section 4.4.

The treatment period duration will be a maximum of 48 weeks, after which participants will enter a 48-week follow-up period. Treatment duration may be shortened (12 or 24 weeks) for 48 week NME combination arms, and/or a response-guided therapy (RGT) arm may be added following planned interim analyses; up to four planned interim analyses will be conducted for each treatment arm (see Section 9.5). Treatment arms that achieve 30% difference, compared to NUC control arm, for HBsAg loss at EOT or follow-up Weeks 12 and 24 (primary endpoint) may be expanded to accrue additional efficacy and safety data and to contribute to Phase 3 design planning as guided by the emerging data, for example, enrichment for HBeAg positive or HBeAg negative participant populations. An expansion may also be triggered prior to EOT, for a treatment arm that gives an early indication of efficacy. The decision criteria to trigger an expansion arm in this case, will be documented as an appendix to the IMC/Scientific Oversight Committee (SOC) charter.

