8.3 ADVERSE EVENTS AND SERIOUS ADVERSE EVENTS

The definitions of an AE or serious adverse event (SAE) can be found in Appendix 2. The adverse events of special interest and disease-related events and/or disease-related outcomes not qualifying as AEs or SAEs are discussed in Section 8.3.6 and Section 8.3.7.

The Investigator and any qualified designees are responsible for ensuring that all adverse events (including assessment of seriousness, severity and causality (see Appendix 2) are recorded on the Adverse Event eCRF and reported to the Sponsor in accordance with instructions provided in this section and in Appendix 2. Procedures used for recording adverse events are provided in Appendix 3.

8.3.1 Time Period and Frequency for Collecting Adverse Event and Serious Adverse Event Information

The method of recording, evaluating, and assessing causality of AEs and SAEs and the procedures for completing and transmitting SAE reports are provided in Appendix 2.

Investigators will seek information on adverse events at each participant's contact. All adverse events, whether reported by the participant or noted by study personnel, will be recorded in the participant's medical record and on the Adverse Event eCRF as follows:

After informed consent has been obtained but prior to initiation of study treatment, only serious adverse events caused by a protocol-mandated intervention should be reported (e.g., serious adverse events related to invasive procedures such as biopsies). Any other adverse event should not be reported.

After initiation of study treatment, all adverse events, regardless of relationship to study treatment, will be reported until the last follow-up visit.

Post-study adverse events and serious adverse events: The Investigator is not required to actively monitor participants for adverse events after their last follow-up visit.

However, if the Investigator learns of any SAE (including a death) or other adverse events of concern that are believed to be related to prior treatment with study treatment, at any time after a participant has been discharged from the study, and the Investigator considers the event to be reasonably related to the study treatment or study participation, the Investigator must promptly notify the Sponsor. For the procedure of reporting, see Appendix 2.

8.3.2 Method of Detecting Adverse Events and Serious Adverse Events

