Appendix 7 Study Details Specific to NUC Control Arm

[figure not shown]
An overview of the nucleos(t)ide (NUC) control treatment arm is shown in Appendix 7-Figure 1.

Participants will continue their background NUC therapy for the 48-week treatment period. At the end of the treatment period, in line with current CHB treatment guidelines, participants will continue NUC treatment during the follow-up unless the NUC discontinuation criteria have been met (see Section 6.8).

Initially, 30 participants will be randomized to the NUC control arm. The subsequent randomization ratio will depend on the number of actively enrolling NME treatment arms, with the stipulation that no more than 17% of participants will be randomly allocated to the NUC control arm.

Participants in the NUC control arm who complete the follow-up Week 48 visit, and continue to meet the study eligibility criteria, may be offered to participate in an expansion cohort of a combination regimen within this study. This will allow access for NUC control participants to an investigational combination regimen that has shown a positive benefit/risk profile, as this is a pre-requisite for an expansion cohort to commence.

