Appendix 13 Study Details Specific to siRNA (RO7445482) + PD-L1 LNA (RO7191863) + NUC Arms

An overview of short interfering RNA (siRNA) + programmed death ligand-1 locked nucleic acid (PD-L1 LNA) + nucleos(t)ide (NUC) treatment arms is shown in Appendix 13-Figure 1.

Participants will receive RO7445482 (also known as DCR-HBVS; 200 mg every 4 weeks [Q4W]) and RO7191863 in addition to their background NUC therapy in one of two treatment arms that will run in parallel.

[figure not shown]
- One treatment arm will evaluate a 24-week treatment duration where RO7445482 (200 mg Q4W) will be given during Weeks 1-24 and RO7191863
 will be given during Weeks 13-24.
- A second treatment arm will evaluate a 36-week treatment duration where RO7445482 (200 mg Q4W) will be given during Weeks 1-24 and RO7191863 will be given during Weeks 25-36.

In both treatment arms, participants will receive their background NUC therapy for the duration of study treatment. At the end of the treatment period, participants will continue NUC treatment during the follow-up unless the NUC discontinuation criteria have been met (see Section 6.8).

Approximately 30 participants will be randomized to each treatment arm.

If a 30% delta for hepatitis B surface antigen (HBsAg) loss is observed at end-of-treatment (EOT) or follow-up Weeks 12 or 24 (primary endpoint) the treatment arm may be expanded to accrue additional efficacy and safety data, and to contribute to Phase 3 design planning.

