The timing of planned interim analyses and RGT below are illustrated based on a 48week treatment duration arm; for arms with shorter treatment duration, the number of the interim analyses as well as the RGT early treatment discontinuations will be adjusted accordingly.

Analysis	Timing of Analysis
First interim analysis	All participants in the study have completed their 12-week visit for a treatment arm or discontinued prematurely
Second interim analysis	All participants in the study have completed their 24-week visit for a treatment arm or discontinued prematurely
Third interim analysis	All participants in the study have completed their 48-week (EOT) visit for a treatment arm or discontinued prematurely
Fourth interim analysis	All participants in the study have completed their follow-up week 12 visit or discontinued prematurely
Primary	All participants in the study have completed their follow-up week 24 visit or discontinued prematurely
Final	The end-of-study for a treatment arm is defined as the date when the last participant completes their follow-up week 48 visit or discontinued prematurely

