5.4 APPENDIX 4 ANALYSIS DETAILS SPECIFIC TO PD-L1 LNA TREATMENT COMBINATION ARM

PD-L1 LNA treatment combination arm specific analysis are listed in this appendix.

The PD-L1 LNA treatment combination arms as follow:

- One treatment arm will evaluate a 24-week treatment duration where siRNA (200 mg Q4W) will be given during Weeks 1-24 and PDL1-LNA will be given during Weeks 13-24.
- A second treatment arm will evaluate a 36-week treatment duration where siRNA (200 mg Q4W) will be given during Weeks 1-24 and PDL1-LNA will be given during Weeks 25-36.

In both treatment arms, participants will receive their background NUC therapy for the duration of study treatment. At the end of the treatment period, participants will continue NUC treatment during the follow-up unless the NUC discontinuation criteria have been met

The detail analysis of the PBMC and FNA data will be cover in the next version of the statistical analysis plan.

Estimand for PDL1-LNA Treatment Combination:

The difference between proportions of HBsAg loss (qHBsAg <0.05 IU/mL) at week 24 follow-up in virologically suppressed adult CHB participants on established NUC therapy, with preserved liver function and without significant fibrosis/cirrhosis, treated with combination therapies

- 1) siRNA (200mg Q4W)+ PDL1-LNA + NUC, with 24 weeks treatment duration
- 2) siRNA (200mg Q4W)+ PDL1-LNA + NUC, with 36 weeks treatment duration

versus NUC, irrespective of adherence to IMP or whether prohibited medication and/or food has been taken.

The detail analysis of the PBMC and FNA data will be cover in the final version of the statistical analysis plan.

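### Adverse events are observed for 72 and 84 weeks in the two PD-L1 arms but 96 weeks in control, and the SAP sets no common window or person-time rate

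*SAP*

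**What the plan says.** Protocol 4.1 gives the follow-up that every arm shares: "The treatment period duration will be a maximum of 48 weeks, after which participants will enter a 48-week follow-up period". Treatment length differs. Protocol Appendix 7, on control: "Participants will continue their background NUC therapy for the 48-week treatment period". Protocol Appendix 13, on arm 8: "One treatment arm will evaluate a 24-week treatment duration". SAP 5.4, on arm 9: "A second treatment arm will evaluate a 36-week treatment duration where siRNA" (the sentence continues with the dosing weeks). Appendix 13-Table 9 is one follow-up schedule for both PD-L1 arms and ends at follow-up Week 48.

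Collection of adverse events follows each arm's own length. Protocol 8.3.1: "After initiation of study treatment, all adverse events, regardless of relationship to study treatment, will be reported until the last follow-up visit".

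SAP 4.5 groups safety output by randomised arm. SAP 4.5.2 starts its list with "All clinical adverse events (AEs), summarized" and goes on to SAEs, AESIs, grade and causality. It names no window, no person-time denominator and no time-to-event method. SAP Section 4 reports categorical variables as counts and percentages. SAP 4.5.1 tabulates duration of dosing but does not link it to event rates. SAP 4.5.3.1 takes the worst on-treatment laboratory grade. SAP 5.4, written for these arms, adds no safety window. SAP 1.2 (Table 2) does adapt the plan for shorter arms, but only for interim analyses and response-guided stopping: "for arms with shorter treatment duration, the number of the interim analyses as well as the RGT early treatment discontinuations will be adjusted accordingly".

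The opening text of Protocol Section 3 says that safety will be compared with control. The objectives table below it speaks only of assessing safety and tolerability.

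**The concern.** A crude percentage with at least one event rises with the time observed. Arms 8 and 9 are observed for less time than the control they are set beside, so a difference can appear, or a real excess can be understated, with no difference in risk. The shorter arms are also the ones that add an immune-acting drug for which Protocol A13.2 reports ALT elevations related to exposure. Protocol Appendix 7 makes a positive benefit/risk profile a condition for opening an expansion cohort, so these tables may inform a real decision.

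**Working it through.** **1. Observation time.** The plan's own figure is a participation of about 2 years (Protocol 4.1.1, SAP 1.2): 8 weeks of screening + 48 + 48 = 104 weeks. That fits a 48-week arm. By the same sum, arm 8 has 8 + 24 + 48 = 80 weeks and arm 9 has 8 + 36 + 48 = 92. From first dose:

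| Arm | Treatment + follow-up | Total | Ratio to control |
|---|---|---|---|
| 8 | 24 + 48 | 72 weeks (504 days) | 0.75 |
| 9 | 36 + 48 | 84 weeks (588 days) | 0.875 |
| Control | 48 + 48 | 96 weeks (672 days) | 1 |

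**2. Effect on a crude percentage.** The documents give no adverse-event rate, so the control's 96-week incidence c is an assumption. With the same constant hazard in every arm, incidence by week t is 1 − (1 − c)^(t/96). Example: c = 0.50 and t = 72 gives 1 − 0.5^0.75 = 0.405.

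| c (control, 96 weeks) | Arm 8 (72 weeks) | Gap | Arm 9 (84 weeks) | Gap |
|---|---|---|---|---|
| 10% | 7.6% | 2.4 | 8.8% | 1.2 |
| 30% | 23.5% | 6.5 | 26.8% | 3.2 |
| 50% | 40.5% | 9.5 | 45.5% | 4.5 |
| 70% | 59.5% | 10.5 | 65.1% | 4.9 |

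In 30 participants the gaps are about 0.7 to 3.2 people in arm 8 and 0.4 to 1.5 in arm 9.

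**3. If events come early.** Let s be the share of the control's cumulative hazard that falls after Week 72. Arm 8 then shows 1 − exp(−H(1 − s)), with H = −ln(1 − c). For c = 50%: s = 25% (constant hazard) gives 40.5%, s = 10% gives 46.4% and s = 5% gives 48.2%. The gap falls from 9.5 to 3.6 and then 1.8 points.

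**4. Scheduled contacts.** Protocol 8.3.1 has events sought at each contact. Counting the adverse-event row of the schedules:

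- Control (Appendix 7-Table 2): 6 on treatment (Day 1, Weeks 4, 12, 24, 36, 48) and 4 in follow-up (Weeks 12, 24, 36, 48) for someone who stays on NUC, since note o keeps the other seven for those who stop. Total 10 in 96 weeks.
- Arm 8 (Appendix 13-Tables 7 and 9): 16 + 11 = 27 in 72 weeks.
- Arm 9 (Appendix 13-Tables 8 and 9): 19 + 11 = 30 in 84 weeks.

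Control follow-up Week 24 is study Week 72 and follow-up Week 36 is study Week 84. Inside the common windows the counts are therefore 6 + 2 = 8 against 27, and 6 + 3 = 9 against 30.

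**5. Laboratory draws.** Post-baseline on-treatment hematology and chemistry: control 3 (Weeks 12, 24, 48), arm 8 15, arm 9 18. Cutting control at Week 24 or Week 36 leaves 2, because control has no such draw at Week 36. Some draws do line up. Counting follow-up days from the end-of-treatment visit, control draws fall on Days 84, 168, 336, 336 + 84 = 420, 336 + 168 = 504 and 336 + 252 = 588. Arm 8 has Days 85, 169, 169 + 168 = 337, 169 + 252 = 421 and 169 + 336 = 505. Arm 9 has Days 85, 169, 253 + 84 = 337, 253 + 168 = 421, 253 + 252 = 505 and 253 + 336 = 589. That is five matched visits for arm 8 and six for arm 9, of which two fall in the arm's treatment period.

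**The case against.** The strongest reply is about ascertainment. With 27 or 30 scheduled contacts against about 10, and 15 or 18 on-treatment draws against 3, arms 8 and 9 have far more chances to record an event. A reader might infer from the durations that these arms will look safer. The documents do not support that: time and contacts push in opposite directions, and nothing in the plan says which is larger. This part of the objection stands.

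It also stands that the sizes rest on assumed rates, that all output is descriptive, that dosing duration is tabulated so the imbalance can be seen, and that interim safety summaries by time point (SAP 4.7.1) give partly aligned looks. The output specifications cited in the SAP are not available and could contain a window. A 10-point gap is also below the standard error of a difference between two arms of 30, about √(2 × 0.25/30) = 13 points at 50%. But it is a systematic shift, which random error does not excuse.

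A reader might also extend the point to efficacy, since 24 weeks after treatment falls at Week 48 or 60 in these arms and Week 72 in control. That does not hold up. Treating the plan's 3% as an annual rate (an assumption), 1 − 0.97^(t/52) gives 2.77%, 3.45% and 4.13% at Weeks 48, 60 and 72. The differences are 4.13 − 2.77 = 1.36 and 4.13 − 3.45 = 0.68 points, against a 30-point target. Longer control time works against the new arms, so the effect is conservative. SAP 5.4 fixes the estimand at that post-treatment visit on purpose.

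**Conclusion.** The gap in the SAP is real. Observation is 72, 84 and 96 weeks, the protocol intends a safety comparison with control, and SAP 4.5.2 sets no common window or person-time rate. From observation time alone, crude percentages would be lower by 2.4 to 10.5 points in arm 8 and 1.2 to 4.9 points in arm 9. This assumes equal constant hazard and a control incidence of 10% to 70% over 96 weeks; early clustering of events shrinks it. These figures isolate one source of distortion and do not forecast the net result, whose direction is unknown because of the denser visits in arms 8 and 9 and any true drug effect. No change to the efficacy analysis follows.

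**What to change.** In SAP 4.5.2, for arms 8 and 9, present adverse-event, SAE and AESI incidence for the arm and control over the same time from first dose: to Week 72 for arm 8 and Week 84 for arm 9. Add events per person-year for full follow-up. At the primary analysis some participants will have only 24 + 24 = 48 or 36 + 24 = 60 weeks, so state the shorter common window used there.

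In SAP 4.5.3.1, do not simply cut control at Week 24 or 36 for the worst-grade tables, which would leave two control draws. Compare at visits scheduled in both arms within the common window, or print the number of scheduled draws per arm beside the table. A footnote with scheduled contacts under the adverse-event tables would serve the same purpose, since a common window does not remove that imbalance.

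The cost is SAP wording and a date cut-off in existing tables, with no new visits, data or participants. The downside is that late control events leave the comparative table; they stay in the full-follow-up output.

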4.5.3 Additional Safety Assessments

Pregnancies:

A listing of pregnancy test outcomes and any other information collected on CRF will be reported.

Liver Imaging Assessment:

The results of abdominal hepatic ultrasound (during treatment and follow-up) will be listed as follows:

- No. of readings taken & reading success rate (n, %)
- Median stiffness (kPa)
- Interquartile range / IQR (kPa)

Concomitant Medications:

The original terms recorded on the participants' eCRF by the Investigator for concomitant medications will be standardized by the Sponsor by utilizing a mapped term and appropriate drug dictionary level.

Concomitant medications will be presented in summary tables and listings and will be flagged for 1) AE's, 2) HBV treatment 3) other

Green tea consumption will be summarized in a separate table.

Medication Error and Overdose:

Overdose (accidental or intentional), medication error will be listed in a separate listing.

Analyses of Documenting Impact of the COVID-19:

The below tables and listing are recommended to access in case study has been impacted due to covid19.

- Listing of Major Protocol Deviations Related to COVID-19 (new listing template including new reason column)
- Summary of Major Protocol Deviations Related to COVID-19

 Summary of Reasons for Major Protocol Deviations Related to COVID-19 (new summary template with deviations categorized by reason)

Based on the above summary tables, the following relevant information can be extracted and should be described in the CSR:

- Number/% of Subjects with major pandemic-related impact on study treatment exposure
- Number/% of Subjects with major pandemic-related impact on primary endpoint assessments (and similarly for other critical study endpoints)

Premature discontinuation from treatment or study-

It is recommended that the number of subjects who prematurely withdraw from treatment or study due to COVID-19 related reasons is described in the relevant CSR sections or in CSR COVID-19 appendix.

The number of subjects with discontinuation due to direct COVID-19 impacts are available from the recommended new TLGs for the Adverse Events.

- Number/% with Suspected/Confirmed COVID-19
- Number/% with Study Treatment Discontinuation due to AEs associated with COVID-19
- Number/% with Study Discontinuation due to AEs associated with COVID-19
- Number/% with Death due to AEs associated with COVID-19

For Statistical Programming team, please refer the document (Safety Analysis Impact of COVID-19 (All Domains) v0.1) guidance for additional TLGs in case moderate to major impact on the study.

Virological Breakthrough/ Relapse:

The number of participants who had virological breakthrough and relapse will be presented by treatment arm as collected on the CRF, a listing will be provided..

